### 10.2 ADVERSE EVENTS

An adverse event is defined as any untoward medical occurrence in a subject administered a medicinal product that does not necessarily have a causal relationship with this treatment. This includes an exacerbation of pre-existing conditions or events, inter-current illnesses, drug interaction, or the significant worsening of the indication under investigation that is not recorded elsewhere in the eCRF under specific efficacy assessments. The reporting period of an AE begins from the time that the subject provides informed consent through and including 30 calendar days after the last administration of BVD-523 (or at the time when a subject begins a new anticancer therapy). Anticipated fluctuations of pre-existing conditions, including the disease under study that does not represent a clinically significant exacerbation or worsening, need not be considered AEs.

The severity of an AE will be graded according to the National Cancer Institute (NCI) Common Terminology Criteria for Adverse Events (CTCAE), version 4.03 with values of Grade 1 to Grade 5 (increased in severity). For AEs not covered by NCI CTCAE, the severity will be characterized as "mild," "moderate," or "severe" according to the following definitions:

- Mild events are usually transient and do not interfere with the subject's daily activities.
- Moderate events introduce a low level of inconvenience or concern to the subject and may interfere with daily activities.
- Severe events interrupt the subject's usual daily activities.

All AE relationship to the study drug, BVD-523, are classified as "unrelated," "possibly related," or "related."

#### **AE Coding**

Any AE including SAE in verbatim term will be coded in accordance with the Medical Dictionary for Regulatory Activities (MedDRA®) dictionary version 17.1 to a system organ class (SOC) and preferred term (PT) within each SOC. Analysis of AEs will then be performed using SOCs and PTs.

Dose Limiting Toxicities, Maximum Tolerated Dose, and Recommended Phase 2 Dose

As specified in Section 3.1, a DLT is defined as a **BVD-523 related toxicity** in the first 21 days of treatment that results in:

- Any treatment-emergent study drug related Grade 3 or Grade 4 non-hematologic toxicity unless clearly and incontrovertibly unrelated to BVD-523. Exceptions are Grade 3 or 4 nausea or vomiting that is controllable by anti-emetics or Grade 3 or 4 diarrhea controllable by optimal therapy such as loperamide. Grade 3 laboratory investigations other than serum creatinine, bilirubin, AST or ALT will not be considered a DLT unless they are associated with clinical manifestations.
- Study-drug related Grade 4 thrombocytopenia that was not present at study entry and that does not resolve within 7 days, unless clearly and incontrovertibly unrelated to BVD-523.
- Febrile neutropenia or Grade 4 neutropenia that was not present at study entry and that does not resolve within 7 days, unless clearly and incontrovertibly unrelated to BVD-523.
- Prolonged myelosuppression or pancytopenia with a hypocellular bone marrow and no marrow blasts lasting for 6 weeks that is not related to disease progression.
- Any study drug related toxicity that results in treatment delays of > 4 days, except when subject is experiencing rash in which case, subject may be off drug for up to 7 days while receiving treatment.

As specified in Section 3.1, the MTD is defined as the highest dose level at which no more than 1 of 6 subjects experiences BVD-523 related DLTs in the first 21 days of treatment. The RP2D may be as high as the MTD and will be determined in discussion with the Clinical Investigators, the Medical Monitor, and the Sponsor. Observations related to pharmacokinetics (PK), pharmacodynamics (PD), and any cumulative toxicity observed after multiple cycles may be included in the rationale supporting the RP2D.

### **Treatment Emergent Adverse Event**

A treatment emergent adverse event (TEAE) is any AE temporally associated with the use of BVD-523 (from BVD-523 initiation until 30 calendar days after the last administration of BVD-523), whether or not considered related to the study drug. If the onset of an AE is missing and the AE resolution date is either after the initial BVD-523 dose date or missing, then the AE will be considered treatment emergent.

## **AE Summaries**

A subject who reported multiple AEs that map to a common PT or SOC is counted only once for that PT or SOC at the highest severity reported and at the greatest relationship to study drug. The number and percentage of subjects who experienced at least one AE as well as subjects who experienced at least one TEAE will be tabulated by SOC and PT with respect to dose level treatment group for each study part. The same tabulation will also be applied to any treatment emergent SAEs and any TEAEs leading to premature discontinuation from the study as well as to any DLTs.

Page 28

<sup>1 All toxicities will be considered related to BVD-523 if they cannot be definitively explained by underlying disease, intercurrent illness or concomitant medications.

The number and percentage of subjects who experience at least one TEAE will also be tabulated by SOC and PT within each dose level treatment group with respect to relationship to study drug (unrelated and at least possibly related [combining events classified as either possibly related or related]) and severity (Grade 1 to Grade 5 and ≥Grade 3). The tabulation by relationship

(unrelated and at least possibly related) will also be applied to any treatment emergent SAEs (TESAEs).

Subject listings will also be provided for all AEs, all SAEs, all AEs leading to early discontinuation from the study, all AEs leading to study drug interruptions and length of interruptions.

Bar graphs of AEs in CTCAE Term will be displayed in decreasing order of incidence from most common to least common. Each bar in the plot will represent an AE in CTCAE Term. Severity of AE (grades) will be embedded in each bar using the percentages of subjects in each AE grade. These plots will be provided for all AEs, TEAEs, treatment-emergent SAEs, and AEs leading to premature discontinuation from the study.

### 10.3 SERIOUS ADVERSE EVENTS AND DEATH

Separate data listings and summaries will be presented for all SAEs and deaths.

### 10.4 LABORATORY EVALUATIONS

Laboratory assessments and change from baseline will be summarized with descriptive statistics by panel, test, dose of BVD-523, and time point. Additionally, abnormal results will be summarized with frequencies and percentages by clinical significance, panel, test, treatment group, and time point. The clinical significance of lab tests will also be summarized by shift tables.

A data listing will display all laboratory test results and findings.

Laboratory evaluations obtained from the following clinical laboratory tests will be collected at Screening, Baseline, Days 8, 15, 22, 29, 36, 43, and, in subjects who continue treatment, every 3 weeks or if clinically indicated thereafter:

- **Hematology** hemoglobin, hematocrit, white blood cells (WBC) count with differential, red blood cells (RBC) count, and platelet count.
- **Blood Chemistry** albumin, alkaline phosphatase (ALP), total bilirubin, calcium, chloride, creatinine, glucose, inorganic phosphorus, potassium, total protein, alanine aminotransferase (ALT), aspartate aminotransferase (AST), sodium, blood urea nitrogen (BUN), uric acid, cholesterol and triglycerides (at screening and first day of Cycle 1).
  - If total bilirubin concentration is increased above 1.5 times the upper normal limit, total bilirubin should be differentiated into direct and indirect reacting bilirubin.
- **Urinalysis** specific gravity, pH, semi-quantitative "dipstick" evaluation of glucose, protein, bilirubin, ketones, leukocytes, and blood. Abnormal findings by dipstick will trigger a full microscopic examination including RBC, WBC, and casts.

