BVD-523 was administered to male and female Sprague-Dawley rats in several toxicology studies: (1) a GLP study for up to 28 days at dose levels up to 50 mg/kg/day twice daily; (2) for up to 14 days at dose levels up to 100 mg/kg twice daily; and (3) for up to 5 days at dose levels up to 150 mg/kg/dose once daily. The incidence and severity of mineralization seen in these studies was dose-dependent and effects were observed in one or more tissues at toxic doses. In animals in which mineralization occurred after treatment with BVD-523, significantly increased serum phosphorus and modestly decreased serum calcium were seen. These effects were not observed in animals in which there was no mineralization. Therefore, the risk of tissue mineralization can be assessed by serum phosphorus and calcium monitoring. A clinical monitoring strategy similar to this was previously employed for related drugs that target the MAPK pathway because those compounds likewise elicited mineralization in rodents.

When BVD-523 was administered to male and female Sprague-Dawley rats for up to 28 days at a dose level of 25 or 50 mg/kg twice daily, BVD-523 was poorly tolerated. Although most clinical signs and clinical pathology findings reversed following 4 weeks of recovery, skin lesions and histopathology findings persisted in many tissues at both dose levels after the recovery. Based on these findings, 25 and 50 mg/kg twice daily dose levels were considered severely toxic. Administration of 12.5 mg/kg twice daily for 28 days was generally well-tolerated by rats of both sexes; however, this dose level was associated with test article-related findings that included (1) swelling in the neck, (2) decreased forelimb strength, (3) multiple clinical pathology findings, and (4) enlarged lymph nodes, spleen, and mammary gland. Based on these observations, the severely toxic dose in 10% of the animals (STD10) for BVD-523

when administered for up to 28 days in Sprague-Dawley rats is 12.5 mg/kg given twice daily (25 mg/kg/day). On Day 28 of the dosing phase, this dose level corresponded with a  $C_{max}$  of 28700 and 15323 ng/mL and AUC0-12 of 264868 and 124341 hr.ng/mL for males and females, respectively.

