### 3.1.4.2 Definition of Dose Limiting Toxicity (DLT)

The DLT is defined using the Common Terminology Criteria for Adverse Events Version 4.0 (CTCAE v4.0) in the first 21 days of treatment. All toxicities will be considered related to BVD-523 if they cannot be definitively explained by underlying disease, intercurrent illness or concomitant medications.

- Any treatment emergent study drug related Grade 3 or Grade 4 non-hematologic toxicity unless clearly and incontrovertibly unrelated to BVD-523. Exceptions are Grade 3 or 4 nausea or vomiting that is controllable by anti-emetics or Grade 3 or 4 diarrhea controllable by optimal therapy such as loperamide. Grade 3 laboratory investigations other than serum creatinine, bilirubin, AST or ALT will not be considered a DLT unless they are associated with clinical manifestations.
- Study-drug related Grade 4 thrombocytopenia that was not present at study entry and that does not resolve within 7 days, unless clearly and incontrovertibly unrelated to BVD-523.
- Febrile neutropenia or Grade 4 neutropenia that was not present at study entry and that does not resolve within 7 days, unless clearly and incontrovertibly unrelated to BVD-523.
- Prolonged myelosuppression or pancytopenia with a hypocellular bone marrow and no marrow blasts lasting for 6 weeks or more that is not related to disease progression.

• Any study drug related toxicity that results in treatment delays of > 4 days, except when patient is experiencing rash in which case, patient may be off drug for up to 7 days while receiving treatment.

All subjects who are not evaluable for toxicity in Cycle 1 due to unrelated AEs will be replaced.

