## 6.5 SAFETY ASSESSMENTS

Safety evaluations will be conducted at baseline, on Days 1, 8, 15, 22, 29, 36, 43, and, in patients who continue treatment, every 3 weeks or if clinically indicated thereafter. These evaluations will include a targeted physical examination, electrocardiography in subjects where clinically indicated and clinical laboratory studies. An ophthalmologic assessment will be conducted at baseline, at the end of study and at other visits by an ophthalmologist if clinically indicated.

The following clinical laboratory tests will be performed:

- **Hematology** (blood sample: EDTA) hemoglobin, hematocrit, white blood cells (WBC) count with differential, red blood cells (RBC) count, and platelet count.
- **Blood Chemistry** (blood sample: serum) albumin, alkaline phosphatase (ALP), total bilirubin, calcium, chloride, creatinine, glucose, inorganic phosphorus, potassium, total protein, alanine aminotransferase (ALT), aspartate aminotransferase (AST), sodium, blood urea nitrogen (BUN) uric acid, cholesterol and triglycerides (at screening and first day of Cycle 1).
- If the total bilirubin concentration is increased above 1.5 times the upper normal limit, total bilirubin should be differentiated into the direct and indirect reacting bilirubin.
- Urinalysis specific gravity, pH; semi-quantitative "dipstick" evaluation of glucose, protein, bilirubin, ketones, leukocytes, and blood and a microscopic examination including RBC, WBC and casts will be performed if the dipstick is abnormal.

Blood chemistry will be analyzed at each trial center by a certified laboratory and a report of the laboratory values will be sent to the trial center. The investigator or designee will review the laboratory report within 24 hours (except during clinic holidays, when review will be performed within 72 hours) after receipt of the results and assess the clinical significance of all abnormal values. Results must be reviewed prior to dosing and appropriate action taken for any clinically significant abnormal values. Values will be documented on the laboratory report until stabilized, or the laboratory value returns to a clinically acceptable range (regardless of relationship to study medication) or baseline. Any laboratory value that remains abnormal at the end-of-study (EOS) and that is considered clinically significant will be followed according to

accepted medical standards for up to 30 days or until resolution of the abnormality or return to baseline.

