Ophthalmologic examinations include best-corrected visual acuity, visual field examination intraocular pressure, external eye examination, and dilated fundoscopy. For additional details refer to study manual. Note: any patient experiencing vision changes must stop taking BVD-523 and have an ophthalmic evaluation. Study drug may be re-started when symptoms resolve.

Toxicity will assessed using the National Cancer Institute Common Terminology Criteria for Adverse Events, Version 4.03.

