### 3 STUDY DESIGN

### 3.1 OVERALL STUDY DESIGN

This study is an open label, Phase 1/2 clinical trial in subjects with AML or MDS. The trial has a dose-escalation phase (Part 1) and a cohort expansion phase (Part 2).

Part 1 – Dose-escalation Phase: The dose-escalation phase is a 3+3 design to determine the dose limiting toxicities (DLTs), maximum tolerated dose (MTD), and recommended Phase 2 dose (R2PD) of BVD-523 given twice-daily. The starting dose of BVD-523 will be 300 mg BID. Treatment will be administered in continuous, sequential 21 day Cycles until disease progression, unacceptable toxicity, or another withdrawal condition is met. Dose-escalation decisions will be based on Cycle 1 data. Within-subject dose escalations are allowed after completing one Cycle at the initial dose, pending complete Cycle 1 data for the dose to be escalated to. The MTD will be determined based on the highest dose associated with no more than 1 DLT in fewer than 6 subjects. Cohorts will be based on 3 subjects, but can be enlarged as deemed necessary by the Safety Monitoring Committee. Once a dose associated with more than 1 DLT in fewer than 6 subjects has been identified, intermediate doses may be examined to obtain a better estimate of the MTD.

Part 2 – Cohort-expansion Phase: Approximately 40 additional subjects will be recruited to one of two groups:

- Group 1: RAS mutant positive AML or MDS  $(n \le 20)$
- Group 2: RAS mutant negative AML or MDS  $(n \le 20)$

Subjects in both groups will receive treatment at the Recommended Phase 2 Dose (RP2D). Subjects will receive twice daily oral doses of BVD-523 in 21-day treatment cycles until disease progression, unacceptable toxicity, or another withdrawal criterion is met. Treatment cycles will occur consecutively without interruption except when necessary to manage adverse events.

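### Laboratory shift tables rest on investigator-judged clinical significance; no planned table shows the change from baseline to worst CTCAE grade

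*SAP*

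**What the plan says.** SAP 10.4 plans four laboratory outputs: descriptive statistics of values and change from baseline by test, dose and time point; counts of abnormal results by clinical significance; shift tables; and a listing of all results. On the third it says: "The clinical significance of lab tests will also be summarized by shift tables". It does not list the categories.

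Protocol 6.5 says who makes the judgment and when: "The investigator or designee will review the laboratory report within 24 hours", with a longer allowance over clinic holidays. That person is to "assess the clinical significance of all abnormal values". No thresholds are given.

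The same protocol section sets a different scale for toxicity: "Toxicity will assessed using the National Cancer Institute Common Terminology Criteria for Adverse Events, Version 4.03". The DLT definition in Protocol 3.1.4.2 also works in grades. One criterion is "Study-drug related Grade 4 thrombocytopenia that was not present at study entry" and does not resolve within 7 days; neutropenia has a parallel criterion. It also carves out an exception: "Grade 3 laboratory investigations other than serum creatinine, bilirubin, AST or ALT will not be considered a DLT" unless there are clinical manifestations.

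On electrolytes, Protocol 1.5.3 concludes from the rat studies that "the risk of tissue mineralization can be assessed by serum phosphorus and calcium monitoring".

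**The concern.** Safety is a primary objective, and the protocol's language for safety is the CTCAE grade. The cytopenia DLT criteria ask whether a grade was already present at study entry, which is a baseline-to-on-treatment grade comparison. The laboratory shift tables do not make that comparison. They use a judgment with no written threshold, made at up to 6 sites.

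Two groups of results are most exposed. The first is blood counts. The protocol's Introduction describes MDS as a disease of peripheral cytopenias, the eligible MDS risk groups come from a score that counts cytopenias, and Protocol 4.3 sets no minimum neutrophil or platelet count. Many patients are therefore likely to enter with abnormal counts and have little room to move on a coarse scale. The second is calcium and phosphorus. The protocol singles them out as the monitor for tissue mineralization, but their Grade 3 changes without clinical manifestations are outside the DLT definition.

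At stake is how clearly the report shows laboratory worsening by dose level and RAS group. This includes worsening after Cycle 1, because Protocol 3.1.4.3 allows cumulative toxicity to inform the recommended Phase 2 dose.

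**Working it through.** The plan states no figure on this point, so there is none to reproduce. The check sets the passages side by side and then adds a small count.

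**Step 1. Is a graded laboratory shift planned anywhere?** SAP 10.4 names clinical significance as the only basis for shifts. The hematology and chemistry table titles in SAP 14.3.4 refer to evaluations and values; none mentions CTCAE grade or worst post-baseline value. The table shells are in a separate attachment, so layouts cannot be checked.

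**Step 2. Do other outputs fill the gap?**
- Change from baseline is summarized by visit with means, medians and ranges. These describe the group and do not pair a patient's baseline grade with the worst grade.
- Under SAP 7.1, an unscheduled value is set aside if a nominal value exists in the same window. The early windows are three days wide (Days 7 to 9, then 14 to 16), so an unscheduled value on Day 11, for example, falls in no window. The worst value can be absent from by-visit summaries.
- DLT tables cover the first 21 days and only events that meet the definition.
- Graded tables of treatment-emergent adverse events (SAP 10.2) include a laboratory change only if it was reported as an adverse event. Protocol 9.1 and SAP 10.2 exempt anticipated fluctuations of the disease that are not a clinically significant worsening. That is the same kind of judgment again.
- The listing holds every result, but tabulates nothing.

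**Step 3. How much can a significance scale miss?** Assumption: three categories (normal, abnormal not significant, abnormal significant), borrowed from the ECG section, SAP 10.6, because SAP 10.4 names none. How grades map to these categories is also assumed, so a range is shown.

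Grades 0 to 4 give 5 × 4 / 2 = 10 possible worsening moves. A category containing k grades absorbs k(k − 1)/2 of them.

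| Not significant | Significant | Moves with no shift |
|---|---|---|
| Grades 1–2 | Grades 3–4 | 1 + 1 = 2 |
| Grade 1 | Grades 2–4 | 0 + 3 = 3 |
| Grades 1–3 | Grade 4 | 3 + 0 = 3 |
| All abnormal grades in one category | (the same) | 4 × 3 / 2 = 6 |

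The range is 2 to 6 of 10. Under every mapping, a move from Grade 0 does show. All the missed moves start from an abnormal baseline, where 6 worsening moves exist (1 to 2, 3 or 4; 2 to 3 or 4; 3 to 4). Among those, the scale misses 2 to 6 of 6. These are counts of possible moves, not of patients; the documents give no baseline distribution of grades.

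**The case against.** A reader might infer that laboratory worsening will vanish from the report. The documents do not support that. SAP 10.4 adds the shift tables to numeric summaries and a full listing. SAP 14.5 adds listings of normal ranges and of abnormal and clinically significant results. SAP 14.3.1 has DLT tables and adverse events by severity and at Grade 3 or higher. A fall from Grade 2 to Grade 4 neutrophils would be in the listing and would feed the change-from-baseline summary. This part of the objection stands in full and limits the point to how results are tabulated.

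Other objections also have force:
- The SAP does not breach the protocol. Protocol 6.5 itself asks for clinical significance, and Protocol 10.3.8 asks only for summaries and listings. The case rests on better method.
- No proportion of affected patients can be given. The documents state no baseline rate of clinically significant cytopenia. If investigators regard disease-related cytopenia as expected and not significant, the scale keeps some room to worsen.
- The argument about an already abnormal baseline is made for blood counts only. Nothing says calcium or phosphorus will be abnormal at entry. For them the gap is the DLT exception and the lack of a graded table. The documents also do not show whether CTCAE v4.03 grades raised phosphorus, the direction seen in animals. Grade 4 changes are not covered by the exception.
- A grade scale has a ceiling too: a patient at Grade 4 at baseline cannot worsen on it.

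Two further inferences should be resisted. The design matters here ("This study is an open label, Phase 1/2 clinical trial in subjects with AML or MDS"), but the trial is single-arm, so unblinded judgment cannot bias a treatment-control contrast. It can affect absolute rates and comparisons across doses or RAS groups. And a grade shift table would not by itself separate drug effect from marrow disease.

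**Conclusion.** The point holds in a limited form. The laboratory shift tables use a judged category without numeric criteria, while the protocol's toxicity scale and laboratory DLTs use CTCAE grades, and no planned laboratory table title indicates a baseline-to-worst-grade display. Grade worsening from an abnormal baseline, and non-DLT Grade 3 calcium or phosphorus changes, may not show as a shift. They are obscured and not tabulated by grade; they are not removed from the report.

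The only size available is the count of 2 to 6 of 10 possible worsening moves, and it depends on the assumed categories and mappings. That many patients have abnormal counts at baseline is a reasonable inference from the disease and eligibility text, not a stated figure. The conclusion also assumes that the unseen table shells do not already contain a graded shift. The priority is low: a useful improvement to safety reporting that does not affect the validity of the trial.

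**What to change.** In SAP 10.4 and the table list in 14.3.4:

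- Base the hematology and chemistry shift tables on baseline versus worst post-baseline CTCAE v4.03 grade, derived by program from numeric results and local normal ranges.
- Include unscheduled values, and state in SAP 7.1 that the nominal-visit selection rule does not apply to the worst-grade derivation.
- Include calcium and phosphorus. Where CTCAE gives no grade for the direction of interest (check raised phosphorus), use low/normal/high shifts against local ranges.
- Keep clinical significance as a supplementary listing.
- Present the table as descriptive, with no claim that it attributes worsening to the drug.

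The cost is one extra derivation and table. Results and normal ranges are already planned for listing in SAP 14.5, so no new data are needed.
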